## 5. CONSIDERATIONS FOR DATA ANALYSES AND DATA HANDLING CONVENTIONS

### 5.1. Study Treatment & Sub-group Display Descriptors

Treatment Group Descriptions			
[RandAll NG]		Data Displays for Reporting	
Code	Description	Description	Order in TLF
A1	GSK2982772 60 mg	GSK2982772 60 mg	2
A2	GSK2982772 120 mg	GSK2982772 120 mg	3
A3	GSK2982772 240 mg	GSK2982772 240 mg	4
P	Placebo	Placebo	1

### 5.2. Baseline Definitions

Baseline definitions are applied to each period.

For all endpoints (except as noted in baseline definitions) the baseline value will be the latest pre-dose assessment with a non-missing value, including those from unscheduled visits. If time is not collected, Day 1 assessments are assumed to be taken prior to first dose and used as baseline.

Unless otherwise stated, if baseline data is missing no derivation will be performed and baseline will be set to missing.

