1. SYNOPSIS

Protocol Title: A single-centre, randomized, double-blind, dose-ascending, placebo-controlled study to evaluate the safety, tolerability, and pharmacokinetics of oral TID doses (one day) of GSK2982772 in Japanese healthy male subjects

Short Title: Phase I study of GSK2982772 in Japanese healthy male subjects

Rationale:

This study is the first administration of GSK2982772 to Japanese. The purpose of this study is to evaluate the safety, tolerability, and pharmacokinetics (PK) of oral doses of TID doses for one day with GSK2982772 in Japanese healthy male subjects. GSK2982772 or placebo will be administered at 0 hr (the first dosing), 7 hr (the second dosing) and 14 hr (the third dosing) on Day 1 in each period. The intention of this study is to provide sufficient confidence in the safety of the molecule to inform progression to further repeat dose studies in patients. The dose range proposed in this study is based on a low starting dose escalating to the highest dose that is intended for the Phase 2b dose range study.

Objectives and Endpoints:

Objectives	Endpoints
To assess the safety and tolerability of TID doses for one day of GSK2982772 in Japanese healthy male subjects	Adverse events (AEs) Change in laboratory values (clinical chemistry, haematology and urinalysis), 12-lead ECG and cardiac telemetry, vital signs (blood pressure, pulse rate, and body temperature) Physical examinations, including neurological examinations
To characterise the PK profile of TID doses for one day of GSK2982772 in Japanese healthy male subjects	Derived PK parameters for GSK2982772, including area under the plasma drug concentration versus time curve over 24 hr (AUC(0-24)) and AUC over each dose interval (i.e. AUC(0-7), AUC(7-14) and AUC(14-24)), maximum observed plasma drug concentration (C _{max}) following each dose, time to maximum observed plasma drug concentration (T _{max}) following each dose, terminal half-life (t _{1/2}) following the third dose, observed trough plasma drug concentrations (C ₀ , C ₇ , C ₁₄ and C ₂₄), where data allow

Overall Design:

This study will be a double-blind with respect to subjects, investigators and site staff (with the exception of the unblinded site pharmacist), TID oral doses for one day,

ascending dose, randomized, placebo-controlled, 4-way crossover study, shown as the table below;

Group	N	Period 1	Period 2	Period 3	Period 4
A	3	Placebo, TID	60 mg, TID	120 mg, TID	240 mg, TID

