2: Follow-up Visit to occur at least 7 days, and no greater than 14 days after last study treatment administration. If a participant withdrew from the study after received GSK2982772 or placebo dose, the safety assessments listed at follow-up visit will be required.

Detailed Time and Events Table for Days 1-4 (common Period1-4)

Procedure ¹	Day -1	Day 1																									
		Pre-dose	0	20 min	40 min	1 hr	1.5 hr	2 hr	3 hr	4 hr	5 hr	7 hr	7 hr 20 min	7 hr 40 min	8 hr	8.5 hr	9 hr	10 hr	11 hr	12 hr	14 hr	14 hr 20 min	14 hr 40 min	15 hr	15.5 hr		
Admission	X																										
Physical Examination	X	X						X				X ⁶													X ⁶		
Hema/Chem/Urinalysis tests	X																										
Vital signs ²		X						X				X ⁶												X ⁶			
12-lead ECG		X						X				X ⁶											X ⁶				
Cardiac telemetry ³		<=====																									
PK blood sampling		X		X	X	X	X	X	X		X	X ⁷	X	X	X	X	X	X	X		X	X ⁷	X	X	X	X	X
Neurological Examination	X							X																X ⁸			
Study Treatment			X									X											X				
Pharmacogenetic Sampling (PGx) ⁴		<=====																									
Meals Served	X							X ⁹			X ⁹											X ⁹					
AE Review ⁵		<=====																									
Concomitant Medication Review		<=====																									
Discharge																											

Procedure ¹	Day 2								Day 3		Day 4
	16 hr	17 hr	19 hr	22 hr	24 hr	28 hr	32 hr	36 hr	48 hr	60 hr	72 hr
Admission											
Physical Examination					X			X	X		X
Hema/Chem/Urinalysis tests											X
Vital signs ²					X				X		X
12-lead ECG					X				X		X
Cardiac telemetry ³	=====>										
PK blood sampling	X	X	X	X	X	X	X	X	X	X	X
Neurological Examination					X				X		X
Study Treatment											
Pharmacogenetic Sampling (PGx) ⁴	=====>										
Meals Served						X ¹⁰		X ¹⁰	X ¹⁰	X ¹⁰	
AE Review ⁵	=====>										
Concomitant Medication Review	=====>										
Discharge											X

1: In this study, baseline is Day -1 and Day 1 pre-dose tests.

2: Vital signs include PR, BPs and temperature.

3: Only 24 hrs following the first dose administration

4: A PGx blood sample will be collected at any time during the study after randomization and provided informed consent for genetic reserch. The participation is optional for each subject.

5: All SAEs will be collected from the signing of the ICF until the follow-up visit at the time points specified. All AEs will be collected from the start of treatment until the follow-up visit at the time points specified.

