6: Physical Examination, Vital signs and 12-lead ECG of 7hr and 14hr time point are to be performed prior to second or third dose.

7: PK blood sampling of 7hr and 14hr time point are to be performed right prior to second or third dose.

8: Neurological Examination of 14hr time point are to be performed prior to third dose.

9: On Day 1, breakfast will be served approximately 2hr after the first dose, lunch will be served between 2 to 3 hr prior to second dose and dinner will be served between 2 to 3 hr prior to third dose.

10: On Day 2-3, meal will be served per unit schedule. Mealtime will be described in SRM.

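### SAP 5.2 treats untimed Day 1 records as pre-dose baseline although three of the four scheduled Day 1 ECG and vital-sign readings follow the first dose: wrong as written, low impact

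*SAP*

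**What the plan says.** SAP 5.2 sets one general rule: "the baseline value will be the latest pre-dose assessment with a non-missing value, including those from unscheduled visits". It adds that "Baseline definitions are applied to each period", so the rule operates four times per subject. The fallback for records without a time follows: "If time is not collected, Day 1 assessments are assumed to be taken prior to first dose and used as baseline". No endpoint, visit type or planned time point is excluded from it.

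Footnote 1 to the schedule in Protocol Section 2 defines baseline more narrowly: "In this study, baseline is Day -1 and Day 1 pre-dose tests". SAP Appendix 2 repeats that footnote, and SAP 2.1 reports no change from the analysis planned in the protocol.

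Doses are "administered at 0 hr (the first dosing), 7 hr (the second dosing) and 14 hr (the third dosing) on Day 1 in each period". On the later Day 1 assessments the protocol schedule says "Physical Examination, Vital signs and 12-lead ECG of 7hr and 14hr time point are to be performed prior to second or third dose" and "Neurological Examination of 14hr time point are to be performed prior to third dose".

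**The concern.** The fallback would be harmless if the only Day 1 assessment were the pre-dose one. Here Day 1 is the dosing day and holds serial safety readings, most of them taken on treatment. A 7 hr or 14 hr reading made before the second or third dose still follows the first dose. A record from 2, 7 or 14 hr with no time would satisfy the SAP 5.2 sentence while failing the baseline definition in both schedules.

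At stake is how ECG and vital-sign changes are reported. If an on-treatment value becomes baseline, every change for that subject in that period is measured from the wrong origin. Where the drug has moved the value, the reported change shrinks toward zero. Safety and tolerability is the first objective, and the QTc flag is read subject by subject, so one misassigned record can decide whether a subject is flagged.

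**Working it through.** The plan gives no figure to reproduce. The check counts scheduled Day 1 assessments before and after the first dose, then traces which outputs use the derived baseline.

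**1. Day 1 marks before / after the first dose**

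| Assessment | Protocol Section 2 | SAP Appendix 2 |
|---|---|---|
| Vital signs | 1 / 3 | 1 / 3 |
| 12-lead ECG | 1 / 3 | 1 / 3 |
| Physical examination | 1 / 3 | 1 / 0 |
| Neurological examination | 0 / 2 | 0 / 2 |
| Total after first dose | 11 of 14 = 78.6% | 8 of 11 = 72.7% |

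The protocol file holds a second copy of the schedule with one more post-dose neurological mark, which gives 12 of 15 = 80.0%. Some table columns have shifted in the extracted text. That can move a mark to a neighbouring hour but does not change the split before and after the first dose.

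For ECG and vital signs together, (3 + 3) / (4 + 4) = 6/8 = 75% of Day 1 readings follow the first dose. No version of the schedule has a Day 1 pre-dose neurological examination; its pre-dose assessment is on Day -1. The row "Hema/Chem/Urinalysis tests" is marked on Day -1 and at 72 hr, with nothing on Day 1, so the fallback does not reach scheduled laboratory data.

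**2. Outputs that use the derived baseline**

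- ECG: Table 2.17 (change from baseline) and the SAP 9.7.2 flag for a QTc increase above 60 msec.
- Vital signs: Table 2.21 (change from baseline).
- Neurological examination: SAP 7.3 plans findings only (Table 2.14, Listing 29), with no change-from-baseline display.
- Physical examination: no display is listed.

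The numerical effect is therefore confined to ECG and vital signs.

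**3. Size when the rule is triggered**

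Let *e* be the difference between the untimed post-dose record and the true pre-dose value. SAP 5.2 does not say which record prevails if a timed pre-dose value also exists. I take the sentence at its word and let the untimed record be baseline.

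- For that subject and period, each derived change equals the true change minus *e*. The untimed record's own change becomes *e* − *e* = 0.
- With 12 subjects per treatment (Protocol 10.1), all contributing, one such record moves the mean change by *e*/12.
- If the record's true QTc increase was above 60 msec, its flag is lost (0 is not above 60) and the mean moves by more than 60/12 = 5 msec.

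The documents do not say how often times will be missing. If none are missing, the effect is nil.

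**The case against.** The strongest defence is that the sentence will rarely operate, and that other text resolves it when it does. Its trigger, time not being collected, most naturally describes a form with no time field, not a single missing entry. SAP 9.4.2 plans to list actual as well as planned times, which suggests that ECG and vital-sign times will be collected. The same section uses planned time for summaries and derived parameters, and SAP Appendix 2 carries the narrower baseline definition. A programmer who reads these together would not call a scheduled 2 hr record pre-dose. The analyses are descriptive, and full ECG and vital-sign listings (Listings 31 and 34) would still show the raw values.

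Most of this stands, and it keeps the impact low. It does not make the sentence correct. The planned-time rule in SAP 9.4.2 yields wherever something else is stated, and SAP 5.2 states something else. SAP 5.2 also admits unscheduled values to baseline, and those have no planned time point. Protocol 9.3.4 calls for two additional ECG readings when a QTcF value meets a discontinuation criterion. An untimed Day 1 repeat of that kind is the record that should least become baseline.

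A reader might infer that the rule could hide changes from the QTc or neurological stopping criteria. The documents do not support that. Those criteria (Protocol 8.1.3 and 8.1.5) are applied during the study by the investigator and Medical Monitor, whereas the SAP derivations are run after database freeze and unblinding (SAP 3.2). Nor is there a neurological change-from-baseline summary to distort. An untimed scheduled Day 1 neurological record would still be wrongly labelled baseline. That holds for scheduled examinations only, since Protocol 9.3.2 also allows unscheduled ones, which could fall before dosing.

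**Conclusion.** The sentence in SAP 5.2 is wrong for this design, and its practical weight is low. When triggered, it can turn an on-treatment ECG or vital-sign reading into baseline, contrary to the definition in both schedules. The damage is limited to the reported changes in Tables 2.17 and 2.21 and the QTc increase flag for the subject and period concerned: a shift of *e* for that subject and *e*/12 in the treatment mean. How often this would happen is unknown and probably small, and there is no effect if times are recorded.

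The conclusion assumes that the sentence is applied as written and that the untimed record displaces any timed pre-dose value. The 3-of-4 count for the physical examination rests on the protocol schedule alone, since the SAP schedule marks only its pre-dose assessment on Day 1. With no display planned for that examination, the discrepancy changes nothing here.

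**What to change.** Replace the fallback sentence in SAP 5.2, before unblinding, with:

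> If actual time is missing, an assessment is eligible as baseline only if its planned time point is Day -1 or Day 1 pre-dose, or, for an unscheduled assessment, if it is documented as taken before the first dose of the period; for the neurological examination the scheduled baseline is Day -1.

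This brings SAP 5.2 into line with footnote 1 of both schedules. The cost is one sentence, because the planned time points are already in the schedule. There is one small loss: an untimed unscheduled Day 1 reading whose relation to dosing is undocumented can no longer serve as baseline. If no other eligible record exists, SAP 5.2 already sets baseline to missing. The sponsor could also confirm that the case report form collects a time for each ECG and vital-sign reading, which would settle how much the point matters in practice.

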### 5.3. Examination of Covariates, Other Strata and Subgroups

#### 5.3.1. Covariates and Other Strata

The list of covariates may be used in descriptive summaries and statistical analyses. Additional covariates may also be considered.

Category	Details
Covariates	See Section 8.1.5.1, describing pharmacokinetic analyses using statistical model

## 5.4. Other Considerations for Data Analyses and Data Handling Conventions

Other considerations for data analyses and data handling conventions are outlined in the appendices:

Section	Component
9.3	Appendix 3: Study Phases and Treatment Emergent Adverse Events
9.4	Appendix 4: Data Display Standards & Handling Conventions
9.5	Appendix 5: Derived and Transformed Data
9.6	Appendix 6: Reporting Standards for Missing Data
9.7	Appendix 7: Values of Potential Clinical Importance

## 6. STUDY POPULATION ANALYSES

### 6.1. Overview of Planned Study Population Analyses

The study population analyses will be based on the Enrolled or Safety population, unless otherwise specified.

Study population analyses including analyses of subject's disposition, protocol deviations, demographic and baseline characteristics, prior and concomitant medications, and exposure and treatment compliance will be based on GSK Core Data Standards. Details of the planned displays are presented in [Appendix 9: List of Data Displays](#).

Display Type	Data Displays Generated		
	Table	Figure	Listing
Subject Disposition			
Subject Disposition for the Subject Conclusion Record	Y		Y
Screening Status and Reasons for Screen Failure	Y		Y
Number of Subjects Enrolled by Country and Site ID	Y		
Subjects for Whom the Treatment Blind was Broken			Y
Planned and Actual Treatments			Y
Protocol Deviations			
Important Protocol Deviations	Y		Y
Inclusion/Exclusion Criteria Deviations			Y
Population Analysed			
Subjects Excluded from PK Population			Y
Demographic and Baseline Characteristics			
Demographic Characteristics	Y		Y
Race and Racial Combinations	Y		Y
Age Ranges	Y		
Medical Conditions and Concomitant Medications			
Medical Conditions			Y
Concomitant Medications			Y
Exposure and Treatment Compliance			
Exposure to Study Treatment			Y

#### NOTES:

- Y = Yes display generated.

### 6.1.1. Details of Planned Study Population Summaries

#### Subject Disposition

##### Subject Disposition for the Subject Conclusion Record

The number and percentage of subjects who completed the study as well as subjects who withdrew from the study will be summarized. Reason for withdrawal will also be summarized for subjects who withdrew from the study. Only the total column will appear.

##### Screening Status and Reasons for Screen Failure

This will be based on Enrolled population. The number and percentage of subjects who passed screening and who failed screening and therefore were not entered into the study will be summarized along with the reasons for failure will be summarized for those subjects who failed screening. Only the total column will appear.

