6.4. Screen Failures

Screen failures are defined as participants who consent to participate in the clinical study but are not subsequently randomized. A minimal set of screen failure information is required to ensure transparent reporting of screen failure participants to meet the Consolidated Standards of Reporting Trials (CONSORT) publishing requirements and to

respond to queries from regulatory authorities. Minimal information includes demography, screen failure details, eligibility criteria, and any SAEs.

Individuals who do not meet the criteria for participation in this study (screen failure judged ineligible) may not be rescreened.

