### 4. ANALYSIS POPULATIONS

Population	Definition / Criteria	Analyses Evaluated
Screened	

• All subjects who have a screening visit will be included

	

• Study Population

Enrolled	

• All subjects who passed screening and enter the study will be included.

• Note screening failures (who never passed screening even if rescreened) and subjects screened but never enrolled into the study (Reserve, Not Used) are excluded from the Enrolled population as they did not enter the study.

	

• Study Population

Safety	

• All subjects who have received at least one dose of study treatment will be included.

	

• Study Population

• Safety

Pharmacokinetic (PK)	

• All subjects in the Safety population for whom a pharmacokinetic sample has been obtained and analyzed will be included.

	

• PK

Refer to [Appendix 9](#): List of Data Displays which details the population used for each display.

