### 9.9.4. Study Population Tables

Study Population Tables					
No.	Population	IDSL / Example Shell	Title	Programming Notes	Deliverable [Priority]
Subject Disposition					
1.1.	Safety	ES1A	Summary of Subject Disposition for the Participant Conclusion Record	ICH E3, FDAAA, EudraCT	SAC
1.2.	Enrolled	ES6	Summary of Screening Status and Reasons for Screen Failure	Journal Requirements	SAC
1.3.	Enrolled	NS1	Summary of Number of Participant by Country and Site ID	EudraCT/Clinical Operations	SAC
Protocol Deviation					
1.4.	Safety	DV1	Summary of Important Protocol Deviations	ICH E3	SAC
Demographic and Baseline Characteristics					
1.5.	Safety	DM3	Summary of Demographic Characteristics	ICH E3, FDAAA, EudraCT	SAC
1.6.	Safety	DM5	Summary of Race and Racial Combinations	ICH E3, FDA, FDAAA, EudraCT	SAC
1.7.	Enrolled	DM11	Summary of Age Ranges	EudraCT	SAC

CONFIDENTIAL

205037

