### 9.9.8. ICH Listings

ICH: Listings					
No.	Population	IDSL / Example Shell	Title	Programming Notes	Deliverable [Priority]
Subject Disposition					
1.	Screened	ES7	Listing of Reasons for Screen Failure	Journal Guidelines	SAC
2.	Safety	ES3	Listing of Reasons for Study Withdrawal	ICH E3	SAC
3.	Safety	SD3	Listing of Reasons for Study Treatment Discontinuation	ICH E3	SAC
4.	Safety	BL2	Listing of Participants for Whom the Treatment Blind was Broken	ICH E3	SAC
5.	Safety	TA2	Listing of Planned and Actual Treatments	IDSL	SAC
Protocol Deviations					
6.	Safety	DV2	Listing of Important Protocol Deviations	ICH E3	SAC
7.	Safety	IE4	Listing of Participants with Inclusion/Exclusion Criteria Deviations	ICH E3	SAC
Populations Analysed					
8.	Safety	SP3A	Listing of Subjects Excluded from Any Population	ICH E3	SAC
Demographic and Baseline Characteristics					
9.	Safety	DM4	Listing of Demographic Characteristics	ICH E3	SAC
10.	Safety	DM10	Listing of Race	ICH E3	SAC
Prior and Concomitant Medications					
11.	Safety	MH3	Listing of Medical Conditions	IDSL	SAC

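### SAP Table 1.2 summarises screen failures on the Enrolled population, which by definition contains none; it should use Screened.

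*SAP*

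**What the plan says.** SAP 6.1.1, under Screening Status and Reasons for Screen Failure, opens: "This will be based on Enrolled population. The number and percentage of subjects who passed screening and who failed screening". The same sentence goes on to describe the subjects to be counted as those "who failed screening and therefore were not entered into the study will be summarized along with the reasons for failure". In SAP 9.9.4 the row for Table 1.2, titled "Summary of Screening Status and Reasons for Screen Failure", has Enrolled in its population column.

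SAP section 4 admits to Enrolled only subjects who passed screening and entered the study, and adds: "Note screening failures (who never passed screening even if rescreened) and subjects screened but never enrolled into the study (Reserve, Not Used) are excluded". Protocol 10.3 carries the same exclusion. Section 4 also defines a Screened population ("All subjects who have a screening visit will be included") and assigns it to study-population analyses.

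In SAP 9.9.8, Listing 1, "Listing of Reasons for Screen Failure", has Screened in its population column.

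**The concern.** The table is meant to count people who failed screening, but its stated population admits only people who passed. The text and the display list agree with each other, so neither corrects the other.

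Table 1.2 is the only planned summary of screen failure. Protocol 6.4 requires a minimum set of screen-failure information so that these subjects can be reported transparently for publication and for regulators' queries, and the programming note for Table 1.2 cites journal requirements. On Enrolled the table cannot serve that purpose. It would also disagree with Listing 1 as soon as one subject failed.

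**Working it through.** The documents state no figure to reproduce here. The check is one of set membership, followed by a short illustration.

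**Membership**

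| Item | Source | Content |
|---|---|---|
| Population for the summary | SAP 6.1.1 text; SAP 9.9.4, Table 1.2 | Enrolled |
| Who is in Enrolled | SAP 4; protocol 10.3 | Passed screening and entered the study |
| Who is kept out of Enrolled | SAP 4; protocol 10.3 | Screening failures; screened but never enrolled |
| Whom the summary must count | SAP 6.1.1 | Passed, and failed with reasons |
| Population for the matching listing | SAP 9.9.8, Listing 1 | Screened |

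1. A subject counted as failed must, under 6.1.1, not have entered the study.
2. A subject in Enrolled must have entered the study.
3. No subject can satisfy both, so the failed count on Enrolled is 0, the passed share is 100%, and there are no reasons to tabulate.

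The remark in the Enrolled definition about rescreening does not change this. Someone who failed once, later passed and entered is not someone who stayed out because he failed. Protocol 6.4 in any case bars rescreening of subjects judged ineligible.

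**Use of Screened across the display list**

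- Study-population tables: 1.1, 1.4, 1.5 and 1.6 use Safety (4); 1.2, 1.3 and 1.7 use Enrolled (3); none of the 7 uses Screened.
- All displays under the SAP 9.9.1 numbering: 7 + 21 + 5 = 33 tables, 5 figures and 37 listings, which makes 75. Only Listing 1 uses Screened.

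**Illustration**

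Let S be the number screened, E the number enrolled and R the number who passed but were held as unused reserves. On Screened, the failure percentage is (S − E − R)/S. Take E = 12, the planned number randomized in protocol 10.1. The documents do not give S or R, so assume R = 0 and vary S:

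| S (assumed) | Failed, on Screened | Failed, on Enrolled as written |
|---|---|---|
| 16 | (16 − 12)/16 = 4/16 = 25% | 0/12 = 0% |
| 20 | (20 − 12)/20 = 8/20 = 40% | 0/12 = 0% |
| 30 | (30 − 12)/30 = 18/30 = 60% | 0/12 = 0% |

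The right-hand column does not depend on S.

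**The case against.** The intent can be read from the SAP. Section 6.1.1 says in words that failures and their reasons are to be shown, section 4 makes Screened available for study-population analyses, and Listing 1 already uses it for the same topic. A careful programmer would probably query the population. Table 1.2 also follows a sponsor standard shell that is not in the documents, so how the table would really be built is not known. Nor is the information lost: in a single-centre study of 12 randomized subjects, failures can be counted from Listing 1.

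The last point stands and keeps the matter minor. The earlier ones make the error easier to catch but do not remove it. The SAP names Enrolled in both places and has no rule for resolving the conflict. Under SAP 9.4.2 the sponsor's reporting standards apply only where nothing else is stated, and here a population is stated. The SAP 6.1 sentence, "The study population analyses will be based on the Enrolled or Safety population, unless otherwise specified", permits an exception, but what is specified for this table is Enrolled. That sentence is not itself at fault.

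It is also fair to say that the display counts do not measure the harm. The other study-population tables have no need of Screened. The error is one table with one wrong population.

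**Conclusion.** The concern holds. As written, Table 1.2 reports 0% failed, 100% passed and no reasons for any number screened. This follows from the definitions alone and needs no assumption. The 25% to 60% range is illustrative and rests on assumed values of S, with E = 12 and R = 0; the true rate cannot be derived from the documents.

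The consequence is an uninformative disposition table that conflicts with Listing 1 if anyone fails screening. Safety, PK and dose-escalation decisions are untouched. The correction is worth making but is low in severity.

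**What to change.** Replace Enrolled with Screened in two places: the SAP 6.1.1 text on screening status, and the population column of Table 1.2 in SAP 9.9.4. The cost is one word in each. Adding Screened to the default sentence in SAP 6.1 would match section 4 but is not essential.

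Two additions are recommended, though the documents do not require them:

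- Give subjects who passed screening but were not entered (unused reserves) their own row. This depends on reserve status being recorded for each screened subject, which the documents do not show.
- Footnote which definition of screen failure the table uses. Protocol 6.4 reads: "Screen failures are defined as participants who consent to participate in the clinical study but are not subsequently randomized". That wording would count a consented, unused reserve as a failure, while the population definitions list reserves separately from failures. The protocol 6.4 count should not be taken as failures plus reserves unless enrolled is stated to mean randomized. Neither document says so, and admission is the day before dosing (protocol 5.1) while the randomization number is assigned on Day 1 (protocol 7.2).
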